3.3 Recruitment

For this retrospective analysis, medical and physiotherapy records of patients with femoral neck fracture immobilization treated at the Saveetha Medical College and Hospital were reviewed.

Records of participants who had completed a four-week intervention program and had documented outcome measures were included in the study. No direct recruitment or prospective enrollment was undertaken.

Data related to inspiratory capacity measured using a volumetric spirometer and blood pressure assessed using a digital sphygmomanometer were extracted from patient records. Outcome measures recorded at baseline (pre-intervention), at the second week and at the fourth week were included for analysis. Confidentiality of patient information was maintained and the study procedures were conducted under the approval and supervision of the institutional ethics committee and the principal investigator.

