2.1 Background & Aims

Femoral neck fractures are a significant source of morbidity and mortality among the aged population. Due in large part to prolonged immobilization and related systemic consequences. Hip fractures among the elderly have increased dramatically worldwide, from 1.7 million in 1990 to an anticipated 6.3 million in 2050. Immobilization following a fracture frequently leads to decreased inspiratory capacity, compromised pulmonary mechanics and altered cardiovascular regulation, which raises the risk of pneumonia, hypertension and delayed functional recovery. Early cardiopulmonary rehabilitation during the immobilization phase is crucial since respiratory infections and cardiovascular problems have been found to be major causes of early mortality after hip fractures.

Due to medical comorbidities and logistical limitations, prolonged bed rest and delays in surgical intervention are still typical in older patients despite advancements in surgical management. These elements worsen hemodynamic instability and pulmonary deconditioning. While respiratory and cardiovascular components receive less attention during early immobility, musculoskeletal recovery is frequently given priority in conventional therapy.

Breathing-based therapies provide a practical and affordable way to deal with these issues. In patients with chronic respiratory diseases, Liuzijue Qigong, a traditional Chinese breathing practice that combines controlled expiration with sound vibration, has been shown to improve lung function, respiratory muscle efficiency and overall quality of life. In a similar vein, Box Breathing is an organized breathing method that has been demonstrated to improve blood pressure control, autonomic balance and lung volumes.

In cardiopulmonary rehabilitation, breathing-based therapies have become more popular because of their ease of use, affordability and viability for older people who are fragile and immobile. Respiratory

efficiency and hemodynamic stability can be enhanced by methods like Box Breathing and Liuzijue Qigong, which are known to affect autonomic regulation, respiratory muscle function and cardiovascular responses. These treatments are especially important for older patients who have suffered femur neck fractures since prolonged immobility frequently results in decreased lung volumes, decreased inspiratory capacity and altered blood pressure control.

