3.2 Participants

This retrospective study included elderly individuals diagnosed with femoral neck fracture who had undergone a period of immobilization and subsequently received either Liuzijue Qi Gong exercise or Box Breathing technique as part of their rehabilitation program. Participants were identified through a review of medical and physiotherapy records from Saveetha Medical College and Hospital. Eligibility was determined based on inclusion and exclusion criteria documented in the clinical records.

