3.4 Administration

Parameter	Liuzijue Qi Gong Exercise Group	Box Breathing Technique Group
Position	Semi-fowlers position or Supine lying or half lying	Semi-fowlers position or Supine lying or half lying
Session duration	20 minutes per session	20 minutes per session
Frequency	Twice daily	Twice daily
Weekly schedule	6 days per week	6 days per week
Total duration	4 weeks	4 weeks
Intervention description	Coordinated slow breathing while expiration producing six distinct sounds are produced: (“XU,” “HE,” “HU,” “SI,” “CHUI,” and “XI”)	Structured breathing cycle consisting of inhaling for a count of four, holding for four, exhaling for four and holding again for four
Rest intervals	Provided as required and documented	Provided between breathing cycles and documented
Supervision	Administered under physiotherapist supervision	Administered under physiotherapist supervision
Outcome assessment points	Baseline (pre-intervention), 2nd week, 4th week	Baseline (pre-intervention), 2nd week, 4th week

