4.1 Primary Outcomes

Statistical analysis will be performed using appropriate statistical software. Descriptive statistics, including mean and standard deviation, will be calculated for the primary outcome variables: Inspiratory capacity (mL) for both intervention groups.

To evaluate changes over time and differences between groups, a mixed-design repeated measures analysis of variance (ANOVA) will be used, with time (baseline, 2nd week, and 4th week) as the within-subject factor and group (Liuzijue Qi Gong exercise and Box Breathing technique) as the between-subject factor. This analysis will determine the effectiveness of the interventions across the different time intervals.

Post-hoc pairwise comparisons with Bonferroni correction will be conducted when significant main effects or interactions are observed. Mauchly's test of sphericity will be applied, and if the assumption of sphericity is violated ($p < 0.05$), the Greenhouse-Geisser correction will be used. A p -value < 0.05 will be considered statistically significant.

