4.3 Missing Data

In the event of missing data due to incomplete clinical records, appropriate statistical handling will be undertaken. Where feasible, missing values will be addressed using mean imputation within the respective intervention group, provided the proportion of missing data is minimal and missing at random. Cases with substantial missing data will be excluded from the final analysis.

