4.4 Informed Consent Forms (ICF)

Written informed consent had been obtained from participants at the time of clinical treatment as part of routine hospital protocol. For the present analysis, waiver of fresh informed consent will be sought from the Institutional Ethics Committee, as the study involves reviewing existing medical and physiotherapy records without direct participant contact.

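### Section 3.3 admits only records of patients who completed four weeks with outcomes, so entry depends on events after treatment start and can bias mean change, and the comparison of techniques if outcome-related loss differs between them

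*Combined protocol and SAP*

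**What the plan says.** Section 3.2 describes a broad group: patients with a femoral neck fracture who "subsequently received either Liuzijue Qi Gong exercise or Box Breathing technique as part of their rehabilitation program". Its eligibility criteria are referred to but not listed. Section 3.3 narrows that group: "Records of participants who had completed a four-week intervention program and had documented outcome measures were included in the study". Section 4.1 then analyses inspiratory capacity by mixed-design ANOVA "with time (baseline, 2nd week, and 4th week) as the within-subject factor and group" as the between-subject factor, and section 4.2 uses a repeated measures ANOVA for blood pressure.

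Section 4.3 deals with gaps inside admitted records in two ways. Where gaps are few and missing at random, "missing values will be addressed using mean imputation within the respective intervention group". Otherwise, "Cases with substantial missing data will be excluded from the final analysis", with no threshold given. The plan has no table of starters and completers, no reasons for stopping, no sensitivity analysis for patients who stopped, and no statement that the results apply to completers only.

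**The concern.** A patient who began either technique and then died, deteriorated, was discharged early or simply stopped never enters the data set. The imputation in section 4.3 cannot reach such a patient, and its exclusion rule removes more.

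Two results are exposed. The first is change from baseline to week 4, which section 4.1 uses to judge effectiveness over time. Losing patients with poor week-4 values makes the average gain look larger; losing those who recovered fast makes it look smaller. The second is the contrast between the techniques, which is distorted only if outcome-related loss operates differently in the two groups.

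Section 2.1 states that "respiratory infections and cardiovascular problems have been found to be major causes of early mortality after hip fractures". This makes outcome-related loss plausible, but it is weak support, because some of those deaths may come before treatment starts.

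**Working it through.** The plan states no sample size, SD, correlation or completion rate, so there is no figure of its own to reproduce. Every number below is an illustration on assumed inputs.

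**Assumptions.** Baseline and week-4 capacity are bivariate normal with correlation r from 0.5 to 0.8. k is the ratio of the week-4 SD to the baseline SD, and k = 1 unless stated. A proportion p is lost. Bias is the completer mean change minus the mean change of all starters, in baseline SDs.

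**Truncation constant.** If the lowest p of a standard normal variable is lost, the mean of the rest rises by c = φ(z)/(1 − p), where z is the p-quantile. At p = 0.20, c = 0.280/0.80 = 0.350. At 5%, 10% and 30%, c = 0.109, 0.195 and 0.497.

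**Bias in mean change, 20% loss.**
- Lowest week-4 values lost: c(k − r). With k = 1, 0.350 × (1 − r) = +0.175, +0.105, +0.070 for r = 0.5, 0.7, 0.8.
- Highest week-4 values lost: the same sizes with negative sign.
- Softer loss, logistic on week 4 with odds of loss multiplied by 2.7 per SD lower (simulation, 2,000,000 draws): about +0.087, +0.052, +0.034.
- Lowest baselines lost: c(rk − 1). With k = 1 this is −0.175, −0.105, −0.070. The sign reverses once k exceeds 1/r, which is 1.25 at r = 0.8 and 1.43 at r = 0.7. The direction therefore depends on SDs that the documents do not give.
- Largest gains lost: −c√(2(1 − r)) = −0.350, −0.271, −0.221.

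On an assumed SD of 500 mL, level-driven loss gives about 17 to 88 mL (0.034 to 0.176 SD), and gain-driven loss up to about 0.35 × 500 = 175 mL. For the lowest week-4 values at r = 0.5, losses of 5%, 10% and 30% give about 0.05, 0.10 and 0.25 SD.

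**Bias in the comparison.**
- Same rate, same mechanism, same spread and correlation in both groups: the two biases are equal and cancel.
- Different rates, loss unrelated to outcome: zero.
- 10% versus 30% loss of the lowest week-4 values: (0.497 − 0.195) × (1 − r) = 0.151, 0.091, 0.060. With the softer logistic loss, 0.081, 0.048, 0.032.
- 20% lost in each group, week-4 related in one only: 0.03 to 0.18.
- Same rate and mechanism, but r = 0.5 in one group and 0.8 in the other: 0.350 × (0.5 − 0.2) = 0.105. An equal rate and mechanism alone do not guarantee a zero.
- Same rate (70% completion) and same logistic slope per mL on the change, but SD of change 300 mL versus 150 mL: biases of +98 and +30 mL, a difference of 68 mL. This is why the association must be read on a standardised scale.
- One common selection rule on the change and a true group difference of 100 mL (SD 200 mL): completion becomes 76% versus 68% and the difference is biased by −13 mL.

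**Would including all starters help?** A likelihood-based mixed model using every baseline has zero bias when loss depends on baseline. It is not always closer. With the lowest 20% at week 4 lost and no week-2 value, its bias is about +0.29, +0.22, +0.17, against +0.175, +0.105, +0.070 for completers. With the largest gains lost, it is −0.29, −0.25, −0.21 against −0.35, −0.27, −0.22, so it is slightly closer.

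**The case against.** Four objections carry weight.

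First, nothing shows that loss was common, related to outcome, or different by technique. This stands: the size may be near zero. A reader might infer that the rule inflates the reported benefit, or favours one technique. The documents support neither inference, because the direction turns on who was lost and that is not reported.

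Second, section 3.4 gives both groups the same positions, session length, frequency, schedule and assessment times, and both are "Administered under physiotherapist supervision". That weakens a claim of differential loss but does not exclude it. The same table shows different breathing tasks (sounded expiration versus breath holds) and different rest arrangements (as needed versus between cycles). It neither shows nor rules out differential loss.

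Third, with no untreated group, mean change is not a treatment effect even with every starter included. This stands and limits what the fix can achieve. It does not excuse the rule, since section 4.1 uses change over time to judge effectiveness and there is no untreated group in which a shared bias could cancel.

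Fourth, a mixed model can be further from the truth than the completer analysis, and its week-4 means extrapolate for patients who died. Both are correct, so the two analyses belong side by side, deaths need separate reporting, and a heavier sensitivity analysis need not be compulsory.

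**Conclusion.** The point holds in conditional form. Entry under section 3.3 depends on events after treatment start, section 4.3 adds to the selection, and no part of the plan measures or acknowledges it. If loss is related to inspiratory capacity, completer-only mean change can be biased in either direction. The comparison of techniques is biased if that loss differs by technique in rate or in its standardised association with change, which includes groups with different spread or correlation. It is unbiased by this route if loss is unrelated to outcome.

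The true size and direction cannot be obtained from the documents. The ranges of 0.03 to 0.18 SD (level-driven) and up to about 0.35 SD (gain-driven) rest on assumed 20% loss, equal SDs and r of 0.5 to 0.8; they show what is possible, not what happened. Records chosen under section 3.3 cannot settle it, but the source records may. This is a cheap improvement that should be made, not a demonstrated error in a result.

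**What to change.** Replace the entry rule in section 3.3 with wording such as: *Every record in which either technique was started and a baseline inspiratory capacity was recorded is included, whether or not four weeks were completed, grouped by the technique first started.* Then:

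- Tabulate starters, completers, deaths and reasons for stopping by technique, and compare baseline values of completers and non-completers.
- Analyse all recorded baseline, week-2 and week-4 values with a likelihood-based mixed model, and report the completer analysis beside it. State that the model relies on loss depending only on recorded values, and that neither analysis is always closer to the truth.
- Report deaths separately, and state that the model's week-4 means implicitly extrapolate for patients who died.
- A delta-adjusted sensitivity analysis is optional.
- If starters cannot be identified from the records, say so and limit the conclusions explicitly to patients who completed four weeks.

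The cost is protocol wording, some added analysis and further extraction from the same source. Sections 3.2 and 3.3 describe the record review in the past tense, so it may have to be reopened. Section 4.4 says a "waiver of fresh informed consent will be sought from the Institutional Ethics Committee", so its scope should be checked against the added records. Some of these will be incomplete, and the pre-post change may look less favourable. No new patient contact is needed.

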3.4 Administration

Parameter	Liuzijue Qi Gong Exercise Group	Box Breathing Technique Group
Position	Semi-fowlers position or Supine lying or half lying	Semi-fowlers position or Supine lying or half lying
Session duration	20 minutes per session	20 minutes per session
Frequency	Twice daily	Twice daily
Weekly schedule	6 days per week	6 days per week
Total duration	4 weeks	4 weeks
Intervention description	Coordinated slow breathing while expiration producing six distinct sounds are produced: (“XU,” “HE,” “HU,” “SI,” “CHUI,” and “XI”)	Structured breathing cycle consisting of inhaling for a count of four, holding for four, exhaling for four and holding again for four
Rest intervals	Provided as required and documented	Provided between breathing cycles and documented
Supervision	Administered under physiotherapist supervision	Administered under physiotherapist supervision
Outcome assessment points	Baseline (pre-intervention), 2nd week, 4th week	Baseline (pre-intervention), 2nd week, 4th week

3.5 Assessment & Outcomes Measures

3.5.1 Primary outcomes

- Inspiratory Capacity -Volume-Oriented Incentive Spirometer
 - To measure inspiratory capacity in elderly participants, post femoral neck fracture immobilization. To objectively monitor changes in pulmonary function.
 - Instructed to inhale slowly and deeply through the mouthpiece after normal expiration.
 - Maximum volume achieved recorded as inspiratory capacity.

3.5.2 Secondary outcomes

- Blood Pressure - Digital Blood Pressure Monitor (Digital Sphygmomanometer)
 - To measure systolic and diastolic blood pressure. To evaluate cardiovascular response to breathing interventions. To monitor physiological changes over the intervention period
 - Automated, non-invasive device using Oscillo metric methods.
 - Consists of inflatable cuff and digital display.
 - Blood pressure recorded after adequate rest

4. Statistical Analysis Plan (SAP)

Descriptive and inferential statistics will be used. Normally distributed data will be presented by mean and standard deviation (SD) and non-normally distributed data will be presented by median and interquartile range. Categorical data will be presented using percentages. SPSS (version 27.0) will be used for all statistical analyses.

4.1 Primary Outcomes

Statistical analysis will be performed using appropriate statistical software. Descriptive statistics, including mean and standard deviation, will be calculated for the primary outcome variables: Inspiratory capacity (mL) for both intervention groups.

To evaluate changes over time and differences between groups, a mixed-design repeated measures analysis of variance (ANOVA) will be used, with time (baseline, 2nd week, and 4th week) as the within-subject factor and group (Liuzijue Qi Gong exercise and Box Breathing technique) as the between-subject factor. This analysis will determine the effectiveness of the interventions across the different time intervals.

Post-hoc pairwise comparisons with Bonferroni correction will be conducted when significant main effects or interactions are observed. Mauchly's test of sphericity will be applied, and if the assumption of sphericity is violated ($p < 0.05$), the Greenhouse-Geisser correction will be used. A p -value < 0.05 will be considered statistically significant.

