4.2 Secondary Outcomes

Secondary outcome analysis will include systolic and diastolic blood pressure parameters to assess cardiovascular responses to the interventions. Descriptive statistics (mean \pm standard deviation) will be computed for each time point within and between groups.

A repeated measures ANOVA will be performed to examine within-group changes across time and between-group differences in blood pressure values. Where significant effects are identified, post-hoc analysis with Bonferroni adjustment will be carried out to explore pairwise differences between baseline, 2nd week, and 4th week measurements. In cases of sphericity violation, the Greenhouse-Geisser correction will be applied. Statistical significance will be set at $p < 0.05$.

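### Baseline inspiratory capacity is used only as a response level: the group main effect carries any baseline gap, and no baseline-adjusted comparison stands beside the group-by-time test

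*Combined protocol and SAP*

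**What the plan says.** For the primary outcome, Section 4.1 specifies a mixed ANOVA "with time (baseline, 2nd week, and 4th week) as the within-subject factor and group (Liuzijue Qi Gong exercise and Box Breathing technique) as the between-subject" term. It names no covariate. Bonferroni pairwise comparisons follow any significant main effect or interaction, and no single term is named as the comparison of techniques.

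The baseline value is there to be used. Section 3.3 says: "Outcome measures recorded at baseline (pre-intervention), at the second week and at the fourth week were included for analysis". Section 4.3 allows for gaps in the records.

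The groups are formed from care already given. Section 3.2 describes patients who "subsequently received either Liuzijue Qi Gong exercise or Box Breathing technique as part of their rehabilitation program". Section 2.1 calls the study randomised, but Sections 3.1 to 3.3 describe a retrospective record review, and this point relies on the latter.

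Section 4.2 has the same structure for systolic and diastolic pressure: "A repeated measures ANOVA will be performed to examine within-group changes across time and between-group differences in blood pressure values". No covariate, change-score model or sensitivity analysis appears in Sections 4 to 4.3.

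**The concern.** With baseline as one level of time, the group-by-time term compares raw changes. It does not use the correlation between baseline and follow-up as efficiently as a covariate would. It also relies on the assumption that, had the techniques been equal, both groups would have changed by the same amount whatever their starting level. Nothing in a record review ensures this.

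The group main effect is a separate problem. It averages the pre-treatment value with the two follow-up values. It therefore dilutes a real effect and turns a difference that existed before treatment into an apparent technique effect.

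At stake is whether a significant result can be read as one technique outperforming the other.

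**Working it through.** The plan gives no sample size, power, SD or correlation, so it has no figure of its own to reproduce.

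**Inputs.** From the plan: the model and alpha of 0.05 (4.1), a pre-intervention baseline (3.3), and non-random groups (3.2). Assumed: two-sided test, equal SDs, compound symmetry, two equal groups of 30 or 50, and baseline-to-follow-up correlation rho from 0.3 to 0.9.

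**1. Precision of the week-4 contrast, baselines similar.** In units of 2·SD²/n, the change contrast has variance 2(1-rho) and the baseline-adjusted contrast 1-rho². The ratio is (1+rho)/2. For an effect that gives the change contrast 80% power, adjusted power is Φ(2.80/√((1+rho)/2) - 1.96). The last column gives n per group for a 0.5 SD difference at 80% power.

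| rho | 2(1-rho) | 1-rho² | ratio | adjusted power | n, change → adjusted |
|---|---|---|---|---|---|
| 0.3 | 1.40 | 0.91 | 0.65 | 93% | 88 → 58 |
| 0.5 | 1.00 | 0.75 | 0.75 | 90% | 63 → 48 |
| 0.7 | 0.60 | 0.51 | 0.85 | 86% | 38 → 33 |
| 0.8 | 0.40 | 0.36 | 0.90 | 84% | 26 → 23 |
| 0.9 | 0.20 | 0.19 | 0.95 | 82% | 13 → 12 |

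**2. Where the gain ends.** An observed baseline gap of d SD multiplies the adjusted variance by about 1+d²/4. Setting (1+rho)/2 × (1+d²/4) = 1 gives d = 2√(2/(1+rho) - 1), which is 1.15 SD at rho 0.5, 0.84 at 0.7 and 0.67 at 0.8. Beyond that gap, adjustment is the less precise of the two.

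**3. Bias with equal techniques and a baseline gap d.**
- Technique chosen on recorded baseline: the expected week-4 gap is rho·d. The change contrast is rho·d - d = -(1-rho)d, and the adjusted contrast is 0.
- Stable group difference: the week-4 gap is d. The change contrast is 0, and the adjusted contrast is d - rho·d = (1-rho)d.

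At rho 0.5 and d = 0.5 SD, each method is wrong by 0.25 SD in the case that does not suit it. Simulated false-positive rates (rho 0.5, 4000 runs, 30 and 50 per group):

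| Why baselines differ | Gap (SD) | Group-by-time | Week-4, baseline-adjusted |
|---|---|---|---|
| Selection on recorded baseline | 0.29 | 7.4%, 10.0% | about 5% |
| Selection on recorded baseline | 0.47 | 14.7%, 20.6% | about 5% |
| Stable difference | 0.3 | 5.0%, 5.2% | 10.5%, 13.1% |
| Stable difference | 0.5 | 4% to 5% | 19%, 28% |

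**4. Group main effect.** The mean of three visits has variance (1+2rho)/3 in the same units, which is 0.667 at rho 0.5. A stable gap enters in full; a gap from selection on baseline enters as d(1+2rho)/3 = 0.667d.
- Stable, d = 0.3, n = 30: SE = √(2 × 0.667/30) = 0.211, z = 1.42, rejection Φ(1.42 - 1.96), about 30%.
- Stable, d = 0.5, n = 50: SE = 0.163, z = 3.06, rejection about 86%.

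Simulation gives 28% to 85% for stable gaps of 0.3 to 0.5 SD and 14% to 49% for selection on baseline. A real effect that is equal at both follow-ups is diluted to two thirds. At rho 0.5 the main effect then needs 95 per group for a 0.5 SD difference, against 63 for the change contrast and 48 with adjustment.

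**The case against.** The strongest reply is that baseline adjustment is no safer here. Without randomisation, which method is biased depends on why baselines differ, and the documents do not say. At a 0.3 SD gap, the adjusted test does worse under a stable difference (10.5% to 13.1%) than the interaction does under selection on baseline (7.4% to 10.0%). This stands. It rules out the tempting stronger reading that the mixed ANOVA is an error which a baseline-adjusted model should replace.

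A reader might also infer that any baseline difference inflates the interaction's error rate. That is not supported. A stable gap leaves it at about 5%, and chance imbalance does not raise the overall type I error; its effect is conditional on the imbalance observed. Inflation requires the choice of technique to depend on recorded baseline, and nothing in the plan says that it did.

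A third inference would be a power gain near 20 points. At rho 0.5 with 30 per group and half the effect present at week 2, simulation gives 69% for the planned interaction and 88% for adjusted week 4. In a repeat of that setting (67% against 87%), an unadjusted week-4 change test reached 77%, so about half the gain comes from choosing one visit. With the full effect at week 2 the figures are 82% and 88%. If the effect fades by half at week 4, the planned test has 69% and week-4 adjustment 33%.

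What the reply leaves untouched is the main effect, which carries the gap under both mechanisms, and the lack of any second analysis that would show whether the conclusion depends on how baseline is handled.

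**Conclusion.** The concern holds in limited form. Section 4.1 gives up some precision when baselines are similar: 25% of the variance at rho 0.5, 10% or less from rho 0.8 upwards, and nothing once imbalance is large. The interaction is open to regression to the mean only if the technique given depended on recorded baseline. Under a stable group difference the planned interaction is the sounder test. Neither analysis deals with other confounders.

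The firmest part concerns the group main effect. Any pre-treatment difference passes into it, in full or in part, and the plan acts on it without limiting how it may be read.

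The algebra in steps 1 to 4 follows from the stated model under equal SDs and compound symmetry. Every magnitude rests on assumed N, SD and rho and is illustrative. This is a worthwhile, cheap improvement, and it does not show the planned analysis to be invalid.

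**What to change.** In 4.1:
- State that the group main effect over all three visits will not be interpreted as a technique effect.
- Prespecify a baseline-adjusted comparison: weeks 2 and 4 as responses, technique by visit, baseline inspiratory capacity by visit as covariate, and the week-4 contrast between techniques named as the quantity of interest.
- Report it beside the planned group-by-time interaction, and claim a technique difference only with a statement of whether the two agree. Where they disagree, say that the answer depends on why the groups started at different levels.

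In 4.2, do the same for systolic and diastolic pressure, each with its own baseline.

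The cost is a few sentences and one more model per outcome, on data that 3.3 already extracts. The downside is a more cautious conclusion if the two analyses disagree.
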